5.2 EXCLUSION CRITERIA

Exclusion criteria include the following:

- Expected discharge to another state, acute care facility, psychiatric facility, or locked facility (including locked skilled nursing facility, jail, or prison) **OR**
- Expected leaving hospital against medical advice (AMA) or actual AMA **OR**
- Homeless **OR**
- On hospice **OR**
- Already enrolled into study during prior discharge in previous year **OR**
- Expected to receive pharmacist-led post-discharge medication management regardless of the trial **OR**
- Patients admitted by admitting or attending Primary Medical Doctors who have a specialty that is not Internal Medicine or Family Medicine **OR**
- Expected post-discharge setting not conducive to the studied medication management intervention **OR**
- Patients admitted with a suspected or confirmed diagnosis of COVID-19.

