5.3 STRATEGIES FOR RECRUITMENT AND RETENTION

Hospital Discharge Study

Eligible pharmacists will be selected by the pharmacy managers at each site. Eligibility includes training in transitions of care and/or post-discharge care.

A daily Epic report will be generated at each site to identify eligible patients. A research assistant will conduct a brief chart review to confirm eligibility before randomizing the patient using REDCap. For quality assurance, operational reports will be obtained from the emergency department and cross-checked with the EIS report to ensure all patients who may be eligible for the study are accurately identified. The study coordinator will stop randomizing patients if the number of patients concurrently receiving the intervention on any given weekday exceeds the workload capacity of pharmacists at each site. Study coordinators will communicate with pharmacists to regularly re-assess the maximum threshold of concurrent patients in the intervention arm. This strategy aims to reduce the potential for pharmacist burnout and to optimize intervention quality.

Once the patient has been randomized to the intervention or control arm, the clinical pharmacist will approach the patients in the intervention arm.

Focus Group/Interviews Study

We will use a purposive sampling design by role and department to determine eligibility. Eligible participants will receive an email from study staff inviting them to participate in the focus groups, and/or interviews. To enhance recruitment, we will offer a \$125 honorarium to nurses and a \$250 honorarium to physicians for their participation in a 60-90 minute focus group or interview.

Time and Motion Study

Pharmacists will be approached for oral consent at the beginning of a clinic day or clinical shift. Potential participants will be approached, given an information sheet, and the nature of the study will be explained. Inclusion Criteria: Pharmacists participating in the PHARM-DC intervention actively seeing patients and responsible for generating the majority of documentation for the clinical visit.

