8.4 STATISTICAL ANALYSES

8.4.1 GENERAL APPROACH

- We will use chi-square tests, Analysis of Variance (ANOVAs), logistic regression, and means/medians for descriptive statistics.
- We will use a 0.05 cutoff for p-values and 95% confidence intervals for statistical significance.

- Our primary statistical analysis will be a two-sided Z test. We will also compare the baseline characteristics of those subjects across both arms to ensure there are no major differences. All enrolled patients will be analyzed.
- We will check for normality and log-transform variables if necessary for skewed distributions.
- We will calculate all-cause unplanned post-discharge utilization within a 30-day period from the date of discharge from an index admission. Post-discharge utilization will include emergency department visits, observation stays, and inpatient readmissions. Planned readmissions will be excluded using the Centers for Medicare and Medicaid's Planned Readmissions Algorithm. The algorithm assesses a dichotomous yes or no outcome of whether each admitted patient has any unplanned readmission within 30 days. In accordance with the CMS algorithm, if a patient has more than one unplanned admission within 30 days of discharge from the index admission, only the first is considered a readmission. If the first readmission after discharge is planned, any subsequent unplanned readmission is not considered in the outcome for that index admission because the unplanned readmission could be related to care provided during the intervening planned readmission rather than during the index admission.

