8.4.7 SECONDARY DATA ANALYSIS: PROPENSITY SCORE ANALYSIS AT BRIGHAM AND WOMEN'S HOSPITAL

Admission medication reconciliation is theorized to be one of the key components of the PHARM-DC intervention that may contribute to reduced 30-day post-discharge utilization. At the Brigham and Women's Hospital (BWH) site, many more patients were eligible for enrollment in the PHARM-DC clinical trial than were actually enrolled due to limited pharmacist staff bandwidth. For this reason, patients who were eligible, yet were not enrolled, did not receive admission medication reconciliation (also known as a "Best Possible Medication History" [BPMH] in the literature).

As a secondary analysis of trial data, we propose to compare patients who were eligible for trial enrollment *and* enrolled to patients who were eligible *and not* enrolled at BWH. We will perform a propensity score analysis to predict enrollment into the PHARM-DC clinical trial at the individual patient-level. Resulting propensity scores will then be used to identify matches between patients at BWH who were eligible and enrolled vs. eligible and not enrolled during the study period for comparison. The outcome of interest is 30-day post-discharge utilization (same hospital).

Data will be retrieved retrospectively from the electronic health record at BWH as previously described in this IRB protocol. Specifically, variables in the propensity model will include:

1. Time of day of hospital admission
2. Day of week of hospital admission
3. Day of week of hospital discharge
4. Admit type
5. Admit service
6. Discharge service
7. Hospital length of stay
8. Discharge location
9. Admissions medications list
10. High-risk medications list at admission
11. Calendar quarter
12. Insurance type
13. Admission source
14. Interaction effect between length of stay *and* day of week of admission

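### Section 8.4.7 sets enrolled or not-enrolled status by patient and gives no index admission for the non-enrolled; read plainly, this biases the comparator's 30-day return rate low

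*Combined protocol and SAP*

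**What the plan says.** Section 8.4.7 proposes a propensity score "to predict enrollment into the PHARM-DC clinical trial at the individual patient-level". The score is then used to match patients who were "eligible and enrolled vs. eligible and not enrolled during the study period for comparison". The outcome is 30-day utilization at the same hospital. Section 8.4.1 counts it from discharge after an index admission and defines the events: "Post-discharge utilization will include emergency department visits, observation stays, and inpatient readmissions". For a non-enrolled patient, section 8.4.7 does not say which admission is the index. It also does not say how to class a patient who was missed at one eligible admission and enrolled at a later one.

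Two other places bear on this. The only exclusion in section 5.2 that concerns earlier contact with the trial is "Already enrolled into study during prior discharge in previous year", so a missed eligible admission is no bar to enrolment later. Patients were missed for lack of capacity: section 8.4.7 says that "many more patients were eligible for enrollment in the PHARM-DC clinical trial than were actually enrolled due to limited pharmacist staff bandwidth", and section 5.3 says that "The study coordinator will stop randomizing patients if the number of patients concurrently receiving the intervention on any given weekday exceeds the workload capacity". Capacity differs from day to day, so a patient missed once may be taken the next time.

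**The concern.** The outcome belongs to a discharge, but group membership is decided by patient over the study period (36 months in the synopsis). An inpatient return to the same hospital can therefore play two parts: it is the event for the missed discharge, and it is a new chance to be enrolled. If the patient is enrolled at the return, the earlier discharge and its event leave the comparator. The enrolled group loses nothing in the same way, because an enrolled patient who returns stays enrolled.

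Comparator membership then depends partly on the outcome. The analysis asks whether admission medication reconciliation lowers utilization. A comparator rate that is too low hides a benefit or makes enrolment look harmful. A propensity score cannot correct this, because the selection happens after the index discharge. None of the 14 listed variables counts prior or later admissions.

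**Working it through.** **The plan's own figures.** Section 8.4.7 gives none. The only related figures are in section 8.2: 27.5% against 25.01%, 4,888 per group, 80% power, two-sided 0.05. The pooled-variance formula n = [1.960·√(2p̄(1-p̄)) + 0.842·√(p₁q₁+p₂q₂)]² / (p₁-p₂)² gives 4,901 per group, and power at 4,888 is 79.9%. The figures reproduce. They are used here only as a source for the baseline rate.

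**Inputs.**
- r, the true comparator rate of same-hospital return: assumed 22% = 27.5% (section 8.2) × 80% (section 8.4.4, which expects at least 80% of patients to return to the study hospitals).
- g, the share of returning patients whose return is an eligible admission: not given; 30-70% assumed. It is below 100% because an ED visit alone is an event but not an enrolable admission.
- f, the share of eligible admissions enrolled, taken also as the chance of enrolment at an eligible return: not given; 10-20% assumed.

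**Formula.** Let a and b be the chances of later enrolment with and without a 30-day event. After later-enrolled patients are removed, the comparator rate is

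r(1-a) / [r(1-a) + (1-r)(1-b)],

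which is below r whenever a > b. Event-free patients can also be admitted and enrolled after day 30, so b is not zero. If the chance L of enrolment after day 30 is the same with and without an event, then 1-a = (1-gf)(1-L) and 1-b = 1-L. The factor 1-L cancels, leaving

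r(1-gf) / (1-r·gf).

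**In counts**, with g = 50% and f = 20%: of 1,000 missed patients, 220 return, 110 of these have an eligible return admission, and 22 are enrolled at it. The comparator keeps 198 events in 978 patients, which is 20.25%, a bias of -1.75 points.

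| f | g | gf | Comparator rate seen | Bias (points) |
|---|---|---|---|---|
| 10% | 30% | 0.03 | 21.48% | -0.52 |
| 10% | 50% | 0.05 | 21.13% | -0.87 |
| 10% | 70% | 0.07 | 20.78% | -1.22 |
| 20% | 30% | 0.06 | 20.96% | -1.04 |
| 20% | 50% | 0.10 | 20.25% | -1.75 |
| 20% | 70% | 0.14 | 19.52% | -2.48 |

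With r = 27.5%, the ends of the range are 0.275×0.97/(1-0.275×0.03) = 26.90% (-0.60) and 0.275×0.86/(1-0.275×0.14) = 24.60% (-2.90).

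**Simulation under no effect of enrolment.** It ran over 36 months with repeat admissions, a 22% event rate, 60% of events being enrolable returns, and enrolment chances of 10 / 20 / 30% at each eligible admission.
- Equal patient risk. The enrolled show 22.1 / 22.2 / 21.8%. Patients never enrolled in the period, indexed at their first missed admission, show 20.9 / 19.9 / 18.7%. When every missed admission is kept and classed by admission, the comparator shows 22.0 / 22.1 / 22.1%, and the bias is gone.
- Unequal patient risk. The enrolled show 30.9 / 28.8 / 27.0%. Classing every admission gives 30.8 / 28.6 / 27.2%. Never-enrolled patients at their first missed admission show 18.8 / 16.4 / 14.9%. Not all of that gap is outcome-dependent removal, because frequent returners also have more chances to be enrolled. Keeping later-enrolled patients but using only the first missed admission gives 21.6 / 21.5 / 21.8%. So the index rule has to treat both groups alike.

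**The case against.** The strongest reply is that the ever-or-never reading is not forced. The mention of the study period may only mark the calendar window from which eligible patients are drawn. Most of the 14 covariates describe one admission (its time and day, service, length of stay, calendar quarter), so the model needs one admission per record. Appendix A also ties its data request to an index admission. Analysts could well class by admission, and the bias would then be absent. This stands as a limit: a reader might infer that the plan knowingly adopts an ever/never-enrolled rule, and the documents do not go that far. But the wording of the comparison points towards patient-level status, and nothing elsewhere sets an admission-level rule.

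A reader might also infer that only patients with an event can leave the comparator. That is not so: event-free patients can be admitted and enrolled after day 30. The bias is downward only if later enrolment is more likely after an event. This is plausible, since an early return adds a chance, but it remains an assumption.

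A much larger bias is tempting too. With f = 50% and g = 70% the formula gives 15.49%, or -6.5 points. But enrolling half of all eligible admissions sits badly with the statement that "many more patients were eligible for enrollment in the PHARM-DC clinical trial than were actually enrolled due to limited pharmacist staff bandwidth", so that corner should not be used.

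The 22% is itself constructed. The 80% is a lower bound, and section 3 leaves observation stays out of the statewide endpoint while the same-hospital outcome includes them. Finally, the 2.49 points in section 8.2 belong to intervention against usual care, a different contrast from enrolled against not enrolled. They are no benchmark for what matters here.

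**Conclusion.** The point holds as a gap in the rule with a predictable direction. On its plain reading, section 8.4.7 lets a 30-day return move a missed patient out of the comparator, and the comparator rate is then too low. The size is about -0.5 to -2.5 points. That rests on a 22% true rate, 10-20% of eligible admissions enrolled, 30-70% of returning patients having an eligible return admission, and enrolment after day 30 equally likely with and without an event. The documents give neither of the two shares, so the range is an illustration and not an estimate. A reader might infer that the trial's main result is at risk. It is not: this is a secondary, observational analysis at one site, and the randomized comparison does not use it.

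**What to change.** Amend section 8.4.7 as follows.

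- Define exposure at the admission, using only information available up to that admission.
- State the index-admission rule for non-enrolled patients. Either take one eligible admission chosen without regard to later events, or take every eligible admission up to and including enrolment. If one admission is used, apply the same rule to both groups: for example, the first eligible admission for everyone, classed by enrolment status at that admission. The last missed admission would not do, because what makes it the last is that no further eligible admission followed.
- Keep a missed index discharge in the comparator even if the patient is enrolled later.
- If patients contribute more than one discharge, use standard errors clustered by patient.
- Optionally, add prior admissions to the propensity model. Appendix A item 6 already lists the count over the preceding three years for extraction. It becomes more useful if the two groups are not indexed by the same rule.

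The cost is SAP wording and programming on records that are to be retrieved retrospectively anyway. The one drawback is that, under the every-admission rule, some patients contribute several discharges and frequent returners carry more weight.

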1.3 SCHEDULE OF ACTIVITIES (SOA)

(1) *Pharmacist-led Hospital Discharge Care Intervention:*

- a. Eligible pharmacists at each study site will be selected to participate in the intervention based on their training in transitions of care.
- b. Using a daily Epic report generated by EIS, a coordinator at each site will identify eligible patients and notify pharmacists. Trial enrollment will occur for eligible patients admitted every day prior from Monday to Friday.
- c. Randomization will be performed via the REDCap (Research Electronic Data Capture) system.
- d. All eligible patients (both arms) will receive the Best Possible Medication History (BPMH)
- e. Patients in the Study arm:
 - i. On hospital day 1, or as soon as possible: Receive an Initial Medication Regimen Assessment. Clinical pharmacists assess regimen appropriateness, assess barriers to medication adherence, start filling out the Actions for Assessing Adherence Barriers worksheet
 - ii. On hospital day 1, or as soon as possible: Receive a Pre-Discharge Intervention, which, depending on the patient condition, might include a: trial to discontinue certain medications during the hospital; discussion of side effects, flags for new medications prescribed, education about critical barriers to adherence.
 - iii. On day of discharge: Receive an At-Discharge Intervention, which may include a brief discussion of medication changes, discussion of side effects, discussion of red flags for new medications. Clinical pharmacists will also consult with inpatient clinicians and pharmacists to discuss the medication list and will ensure that the e-prescribing is done appropriately.
 - iv. 1-3 days after discharge: Receive a Post-Discharge Intervention, which includes a call with a patient to discuss the patient's regimen, discussion of side effects, red flags of new medications, a motivational interview, a discussion of barriers to adherence. Other tasks might include a phone call with the patient's primary care physician.
 - v. After initial phone call: Some patients, depending on need, might receive a second phone call if needed, a video visit, clinic visit with pharmacist, embedded mental health.
 - vi. For any of the above-mentioned activities, patients may be contacted by pharmacists over the phone instead of in-person to reduce COVID-19 exposure to patients, caregivers, and pharmacists.
- f. Patients in the Control arm:

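### The BWH propensity score uses covariates fixed only at discharge, after the exposure has begun; if enrolment changes the stay, the matched contrast is biased, but length of stay cannot simply be dropped

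*Combined protocol and SAP*

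**What the plan says.** Section 8.4.7 starts from the idea that "Admission medication reconciliation is theorized to be one of the key components of the PHARM-DC intervention". It notes that many eligible BWH patients were not enrolled because pharmacist capacity was limited, and that they did not receive the BPMH. For the comparison, "We will perform a propensity score analysis to predict enrollment into the PHARM-DC clinical trial at the individual patient-level"; the scores are then used to match enrolled with eligible non-enrolled patients. The outcome is 30-day same-hospital utilization after discharge.

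The list of model terms includes "Day of week of hospital discharge" (item 3), discharge service (item 6), "Hospital length of stay" (item 7), "Discharge location" (item 8) and the interaction of length of stay with admission weekday (item 14). The other nine (items 1, 2, 4, 5 and 9 to 13) are known at admission.

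On timing, section 1.3 states: "Trial enrollment will occur for eligible patients admitted every day prior from Monday to Friday". It gives the BPMH to both arms and, for the study arm, says: "On hospital day 1, or as soon as possible: Receive a Pre-Discharge Intervention". Section 9.1.1, under minimal risk, puts the medication history before randomisation.

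Section 8.4.7 does not say why discharge-time terms are used, does not state that enrolment is assumed to leave them unchanged, and plans no analysis restricted to admission-time variables.

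**The concern.** A propensity score should describe patients as they stood when exposure began. Here five of the 14 terms take their values later. If enrolment alters the stay, matching on it does two things. It removes any effect of enrolment that runs through the stay. It also pairs unlike patients: when enrolment shortens stays, an enrolled patient with a four-day stay would have stayed longer without enrolment, and so tends to be sicker than the four-day control. If severity is not fully captured by the other terms, that difference appears as a difference in utilization.

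At stake is the protocol's planned estimate for the BPMH component. Both trial arms receive the BPMH, so the randomised contrast cannot isolate it and would not reveal an error here.

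**Working it through.** Section 8.4.7 gives no sample size, target effect or power, so there is no figure to reproduce. The check compares timing and then illustrates size.

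**1. Timing.** Reading section 1.3 as a weekday list of patients admitted the day before, the sequence is: admission, listing, BPMH, randomisation, study-arm work from hospital day 1 or soon after, discharge. Items 3, 6, 7, 8 and 14 are fixed at the last step.

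**2. Size if enrolment changes the stay.** All inputs are assumptions, except the 27.5% baseline, which is borrowed from section 8.2 for scale. Let U be unmeasured severity (mean 0, SD 1), A enrolment (independent of U), e noise (SD 1) and b the effect of enrolment on log stay:

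- log stay = log 4 + 0.5U + 0.5e + bA
- P(utilization) = 0.275 + 0.06U, with no effect of A

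At a given stay, U changes by 0.5 / (0.25 + 0.25) = 1.0 per unit of log stay. So the false risk difference after matching on stay is −b × 1.0 × 0.06:

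- stay 10% shorter: 0.105 × 0.06 = +0.63 points
- stay 20% shorter: 0.223 × 0.06 = +1.34 points
- stay 10% longer: −0.095 × 0.06 = −0.57 points
- stay 20% longer: −0.182 × 0.06 = −1.09 points
- stay unchanged: 0

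Simulation of this model (2 million patients per scenario) gave +0.66, +1.39, −0.72, −0.95 and +0.15. The unadjusted differences in the same runs were +0.03, +0.02, −0.13, +0.14 and +0.14, which are noise around a true zero. The standard error is about √[0.275 × 0.725 × (1/620,000 + 1/1,380,000)] = 0.07 points, with 31% enrolled.

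With an illustrative true effect of −2.5 points, matching on stay gave −1.83 (10% shorter), −1.22 (20% shorter) and −3.61 (20% longer).

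**3. Sensitivity to the severity links.** Take log stay with 0.5 on severity and residual SD 0.4 (variance 0.25 + 0.16 = 0.41), a log-odds slope of 0.45 for utilization, and about 27% with utilization. For b = −0.10 the approximation is 0.10 × (0.5/0.41) × 0.45 × 0.27 × 0.73 = +1.1 points; simulation gave +1.0. Severity there explains 0.25/0.41 = 61% of the variance of log stay, which is strong. Holding that variance at 0.41:

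- 20% explained: severity coefficient √(0.2 × 0.41) = 0.286, result +0.6 points
- 10% explained: severity coefficient √(0.1 × 0.41) = 0.202, result +0.4 points

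**4. Size if length of stay is simply dropped.** Keep the model of step 2, let enrolment leave the stay unchanged, and make longer-stay patients more likely to be enrolled. Omitting stay gave +1.5 points (log-odds of enrolment rising 0.5 per unit of log stay) or +2.75 (rising 1.0). Matching on stay gave +0.06 and +0.02. With the weaker selection and a 10% shorter stay, omission gave +1.49 and matching on stay +0.67.

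**5. Risk-set matching.** With a 15% chance of enrolment on each hospital day and no true effect, no adjustment gave about +4.9 points. Matching on stay gave about 0 if the stay was unaffected, and +0.6 or −0.6 if enrolment shortened or lengthened it. Matching each enrolled patient, on the day of enrolment, with patients still in hospital and not yet enrolled stayed within about 0.02 points of zero in all three cases. Over a further set of assumed inputs, omission left +1 to +5.6 points and risk-set matching stayed within 0.1 point of zero.

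Steps 2 to 4 match on stay alone. The plan matches on a 14-term score, which balances stay on average, so the mechanism carries over, but the size would differ.

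**The case against.** **Length of stay is there for a reason.** Capacity was limited and enrolment ran Monday to Friday, so a short weekend stay could end before enrolment was possible. Item 14 fits that mechanism. Step 4 shows that ignoring it can cost more than matching on stay does. This stands: the term is a trade-off, and the remedy must replace what it does.

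**Discharge service and location may stand in for eligibility.** Sections 5.1 and 5.2 define eligibility partly by the ward of discharge and the expected destination, and section 5.3 has charts reviewed before randomisation. In retrospective records, the actual service and destination may be the nearest proxies. Both groups are already meant to be eligible, so this does not justify the terms in the main model, but it is a good reason to keep the present list as a sensitivity analysis.

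**No effect on the stay is documented.** A reader might infer that the contrast is biased even with random enrolment. The protocol does not support that: it nowhere says that the BPMH or PHARM-DC changes the stay, and with no change there is no bias from this source. Nor does it rule a change out. Study-arm work may include stopping medications in hospital and consulting inpatient clinicians on the day of discharge.

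**Severity may be partly measured.** Admission type, service, source and medication lists may capture some of it, which would shrink the figures.

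**Conclusion.** The point holds conditionally. Five of the 14 propensity terms are fixed after exposure begins, and the present list is sound only if enrolment leaves them unchanged, an assumption that section 8.4.7 does not state. For a 10% change in stay and no true effect, the false difference is roughly 0.5 to 1.0 points, down to about 0.4 under the weakest link tried. Its sign is opposite to the change in stay. These figures rest on assumed severity links, and the actual direction and size are unknown.

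Two stronger readings should be avoided. One is that the five terms should just be deleted; dropping length of stay alone could leave more bias than it removes. The other is to express the bias as a share of the 2.5-point design effect. That effect belongs to the randomised comparison on same-state utilization, while section 8.4.7 compares different groups on same-hospital utilization and states no target.

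This is a single-site, non-randomised secondary analysis. The randomised primary result is unaffected.

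**What to change.** For the main 8.4.7 analysis:

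- Build the score from admission-time covariates only: items 1, 2, 4, 5 and 9 to 13.
- Combine it with risk-set matching. Pair each enrolled patient, on the hospital day exposure began, with an eligible patient still in hospital and not enrolled by that day. State whether that day is the BPMH or the enrolment date, since the BPMH comes first.
- Do not exclude a candidate control because of later enrolment. That uses future information and brings the opportunity-to-enrol problem back. Report how many controls are later enrolled.
- Do not drop length of stay without the risk-set step.
- Keep the present 14-item list as a sensitivity analysis, and state that it assumes enrolment leaves the stay and discharge variables unchanged.

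The cost is SAP wording, some reprogramming and slightly fewer matches. Appendix A lists index admission and discharge dates but no BPMH or enrolment date, so that date must be retrieved for enrolled patients from trial records. No new patient contact is needed.
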